Revision: C State: Released ECO No: ca-00000172 Effective Date: 19-Sep-2019

Study Synopsis

Study Device	M22 intense pulsed light (IPL) module is a class II device with an FDA clearance (K142860) for benign cutaneous vascular lesions, including erythema of rosacea and facial telangiectasia.		
Protocol number	LUM-VBU-M22-IPL-17-01		
Study Title	Effectiveness of Intense Pulsed Light (IPL) for improving signs and symptoms in Dry Eye Disease (DED) due to Meibomian Gland Dysfunction (MGD)		
Study design	Multi-center, prospective, randomized, sham-controlled, superiority, non-significant risk		
Projected Study period	Initiation Date: January 15, 2018 Completion Date: July 1, 2018		
Study population	Up to 83 male or female subjects, aged 22-85 with signs and symptoms of DED caused by MGD Enrollment will continue until at least 10 subjects without skin rosacea are enrolled.		
Investigational device	Lumenis [®] M22 system with the IPL handpiece		
Study Duration	From screening to termination, each subject will participate in the study for 10-11 weeks (depending on whether screening & enrollment occurred on the same day or up to 1 week later) The total study duration from the screening of the first subject to termination of the last subject is estimated to be 75 weeks.		
Main Inclusion Criteria	 Tear break-up time (TBUT) ≤ 7 seconds MGS ≤ 12 for 15 glands in the lower eyelid At least 5 non-atrophied meibomian glands in the lower eyelid Symptoms self-assessed using the OSDI questionnaire ≥ 23 		
Detailed Inclusion Criteria:	 Subject is able to read, understand and sign an IC form 22-85 years of age Fitzpatrick skin type I-IV Subject is able and willing to comply with the treatment/FU schedule and requirements In the study eye, TBUT ≤ 7 seconds (PMID: 21450918) In the study eye, MGS ≤ 12 (PMID: 2222996) 		

[figure not shown]
protocol for M22 Dry Eye

DOC No.: 1009490

Revision: C State: Released ECO No: ca-00000172 Effective Date: 19-Sep-2019

	In the study eye, at least 5 non-atrophied meibomian glands in the lower eyelid
	• Symptoms self-assessed using the OSDI questionnaire \geq 23 (PMID: 20065224)
	Fitzpatrick skin type V or VI
	Contact lens wear within the month prior to screening
	Unwilling to discontinue use of contact lenses for the duration of the study
	Ocular surgery or eyelid surgery, within 6 months prior to screening
	Neuro-paralysis in the planned treatment area, within 6 months prior to screening
	Other uncontrolled eye disorders affecting the ocular surface, for example active allergies
	Current use of punctal plugs
	Pre-cancerous lesions, skin cancer or pigmented lesions in the planned treatment area
	Uncontrolled infections or uncontrolled immunosuppressive diseases
	Subjects with ocular infections, within 6 months prior to screening
	• Prior history of cold sores or rashes in the perioral area or in the planned treatment area that could be stimulated by light at a wavelength of 560 nm to 1200 nm, including: Herpes simplex 1 & 2, Systemic Lupus erythematosus, and porphyria
	• Within 3 months prior to screening, use of photosensitive medication and/or herbs that may cause sensitivity to 560-1200 nm light exposure, including: Isotretinoin, Tetracycline, Doxycycline, and St. John's Wort
Main Exclusion	Over exposure to sun, within 4 weeks prior to screening
Criteria:	Use of prescription eye drops for dry eye, within 7 days prior to screening, excluding artificial tears and glaucoma drops
	Radiation therapy to the head or neck, within 12 months prior to screening
	Planned radiation therapy, within 8 weeks after the last treatment session
	Treatment with chemotherapeutic agent, within 8 weeks prior to screening
	Planned chemotherapy, within 8 weeks after the last treatment session
	• New topical treatments within the area to be treated, or oral therapies, within 3 months prior to screening- except over-the-counter acetaminophen-based analgesics for pain management, new oral omega 3 fatty acid supplements and topical artificial tears
	Change in dosage of any systemic medication, within 3 months prior to screening
	 Anticipated relocation or extensive travel outside of the local study area preventing compliance with follow-up over the study period
	Legally blind in either eye
	History of migraines, seizures or epilepsy
	Facial IPL treatment, within 12 months prior to screening
	 Any thermal treatment of the eyelids, including Lipiflow, within 6 months prior to screening
	Expression of the meibomian glands, within 6 months prior to screening

QF-1044440 Rev. D	Global Clinical Study Report Template	GEN-0010523	Effective Date: July-2017

	 In either eye, moderate to severe (Grade 3-4 on the EFRON scale) inflammation of the conjunctiva, including: allergic, vernal or giant papillary conjunctivitis
	 In either eye, severe (Grade 4 on the EFRON scale) inflammation of the eyelid, including: blepharochalasis, staphylococcal blepharitis or seborrheic blepharitis
	 Ocular surface abnormality that may compromise corneal integrity in either eye (e.g., prior chemical burn, recurrent corneal erosion, corneal epithelial defect, Grade 3 corneal fluorescein staining, or map dot fingerprint dystrophy)
	 Eyelid abnormalities that affect lid function in either eye, including: entropion, ectropion, tumor, edema, blepharospasm, lagophthalmos, severe trichiasis, and severe ptosis
	 Any systemic condition that may cause dry eye disease, including: Stevens-Johnson syndrome, vitamin A deficiency, rheumatoid arthritis, Wegener's granulomatosis, sarcoidosis, leukemia, Riley-Day syndrome, systemic lupus erythematosus, and Sjögren's syndrome
	• Unwilling or unable to abstain from the use of medications known to cause dryness (e.g., isotretinoin, antihistamines) throughout the study duration. Subjects must discontinue these medications for at least 1 month prior to the baseline visit.
	Any condition revealed whereby the investigator deems the subject inappropriate for this study
	Primary objectives TBUT estimated at the single FU (Between 4 weeks -3 days and 4 weeks + 7 days after the final treatment)
Objectives	Measurement of TBUT will be implemented using FUL-GLO® fluorescein ophthalmic strips. Three successive readings will be taken and averaged to a single value.
	Secondary objectives Self-evaluation of OSDI at the single FU, using the OSDI questionnaire Self-evaluation of Eye Dryness Score (EDS) at the single FU, using a VAS
	Primary endpoint:
	The difference in the change of TBUT from BL to FU, between eyes in the study arm and eyes in the control arm
Criteria for Evaluation	The improvement of TBUT in eyes of the study arm is larger than the improvement of TBUT in eyes of the control arm, where improvement is defined as a positive change of TBUT from BL to FU
	Secondary endpoints
	The difference in the change of OSDI from BL to FU, between subjects in the study arm and subjects in the control arm
QF-1044440 Rev. D	Global Clinical Study Report Template GEN-0010523 Effective Date: July-2017

	The difference in the change of EDS from BL to FU, between subjects in the study arm and subjects in the control arm			
	The improvement of OSDI in the study arm is larger than the improvement of OSDI in the control arm, where improvement is defined as a negative change of OSDI from BL to FU			
	The improvement of EDS in the study arm is larger than the improvement of EDS in the control arm , where improvement is defined as a negative change of EDS from BL to the FU			
	• The difference in the proportion of eyes with normal TBUT (TBUT >10 sec) at FU, between eyes in the study arm and eyes in the control arm			
Exploratory	• The difference in the proportion of subjects with normal OSDI (OSDI < 23) at FU, between subjects in the study arm and subjects in the control arm			
effectiveness endpoints	• The difference in eyelids appearance, as qualitatively evaluated by the study investigator, between eyes in the study arm and eyes in the control arm			
	• The difference in the percentage of area loss of meibomian glands, as evaluated using meibography, between eyes in the study arm and eyes in the control arm			
	• The difference in the change of MGS from BL to FU, between eyes in the study arm and eyes in the control arm			
	Throughout the study:			
	• the difference in the incidence of ocular adverse events, between subjects in the study arm and subjects in the control arm			
	• the difference in the incidence of non-ocular adverse events, between subjects in the study arm and subjects in the control arm			
	• the difference in the incidence of unanticipated serious adverse events, between subjects in the study arm and subjects in the control arm			
Safety Endpoints	At the treatment sessions-			
	• the difference in the change of bio-microscopy examinations pre- and post- treatment, between subjects in the study arm and subjects in the control arm			
	• the difference in the self-assessment of pain/discomfort during IPL administration, between subjects in the study arm and subjects in the control arm			
	• the difference in the self-assessment of pain/discomfort during MGX, between subjects in the study arm and subjects in the control arm			
QF-1044440 Rev. D	Global Clinical Study Report Template GEN-0010523 Effective Date: July-2017			

Т

Г

Description: LUM-VBU-M22-IPL-17-01_Protocol - Clinical study protocol for M22 Dry Eye

Revision: C State: Released ECO No: ca-00000172 Effective Date: 19-Sep-2019

Screening and baseline (BL) visit	Subjects will sign the IC form within one week of passing an informed consent process and having been provided the informed consent form (ICF). After signing the ICF, subjects will undergo the following baseline (BL) assessments, in the specified order:
	1. Three consecutive measurements of tear break-up time (TBUT) in both eyes
	 Routine ophthalmology tests in both eyes, including: biomicroscopy, best-corrected visual acuity (BCVA) and intra-ocular pressure (IOP)
	3. Ocular Surface Disease Index (OSDI), self-assessed using an OSDI questionnaire
	4. Eye dryness score (EDS), self-assessed using a visual analog scale (VAS)
	5. High resolution close-up photos of both eyes, including: the iris, lid margins and eyelashes
	6. Meibography of the upper and lower eyelids in both eyes
	7. Meibomian gland secretion (MGS) score in 15 glands of the lower eyelid in both eyes
Randomization	Eligible subjects will be randomized 1:1 to a study arm or to a control arm
	• The randomization process will adopt a blocked randomization strategy, using random block sizes of 2 and 4
	Four (4) treatment sessions, 2 weeks (-3 days, + 7 days) apart.
	Each treatment session will consist of the following procedures, in the specified order:
	 Subject's report of the daily usage (frequency and dose) of eye drops, warm compresses and lid hygiene since the previous visit
	Pre-treatment biomicroscopy with the slit lamp (observation of lid margins, eyelashes, conjunctiva)
Treatment	3. In the study arm:
schedule	Active IPL administered on the malar region (from tragus to tragus, below the lower eyelids, including the nose)
	In the control arm:
	Sham IPL administered on the same facial areas
	4. Meibomian gland expression (MGX) of the upper and lower eyelids in both eyes
	5. Post-treatment biomicroscopy with the slit lamp
	6. Self-assessment of pain/discomfort during IPL administration, using a VAS

Description: LUM-VBU-M22-IPL-17-01_Protocol - Clinical study protocol for M22 Dry Eye

Revision: C State: Released ECO No: ca-00000172 Effective Date: 19-Sep-2019

	7. Self-assessment of pain/discomfort during MGX, using a VAS
	There will be a single follow-up (FU) visit, which will occur 4 weeks (-3 days, + 7 days) after the final treatment session. Subjects will undergo the following assessments, in the specified order:
	 Subject's report of the daily usage (frequency and dose) of eye drop, warm compresses and lid hygiene since the previous visit
	2. Three consecutive measurements of TBUT in both eyes
Follow-up (FU)	3. Routine ophthalmology tests in both eyes, including: biomicroscopy, BCVA and IOP
visit	4. OSDI, self-assessed using an OSDI questionnaire
	5. EDS, self-assessed using a VAS
	6. High resolution close-up photos of both eyes, including: iris, lid margins and eyelashes
	7. Meibography of the upper and lower eyelids in both eyes
	8. Meibomian gland secretion (MGS) score in 15 glands of the lower eyelid in both eyes
Safety outcome measures	 incidence of non-ocular adverse events throughout the study incidence of ocular adverse events throughout the study incidence of unanticipated serious adverse events throughout the study self-assessment of pain/discomfort of IPL in treatment sessions (using a VAS) self-assessment of pain/discomfort of MGX in treatment sessions (using a VAS)
Covariates	 Baseline TBUT (continuous) Baseline skin rosacea (4-point scale)
	The following assumptions were used to calculate the original sample size:
Sample Size	(1) In the study arm, the change of TBUT from BL to FU $\approx 5 \pm 5$ sec (2) In the control arm, the change of TBUT from BL to FU $\approx 1 \pm 5$ sec (3) A type I error of 0.05 (two-tailed test) (4) A type II error of 0.2 (power = 0.8) (5) A 1:1 ratio of Treatment to Control
	With these assumptions, the minimal sample size was calculated to be 50 evaluable subjects (100 evaluable eyes): 25 subjects (50 eyes) in the control arm and 25 subjects (50 eyes) in the study arm.
	Assuming a dropout rate of 15%, the anticipated number of enrolled subjects was 59. Assuming a screening failure rate of 15%, the anticipated total number of screened subjects was 69.

	Energy to Healthcare I-VBU-M22-IPL-17-01_Protocol - Clinical study 2 Dry Eye	DOC No.: 1009490 Revision: C State: Released ECO No: ca-00000172 Effective Date: 19-Sep-2019
	After study initiation (but before any data were unmasked) it was found that 8 IPL patients at site were not treated in accordance with the protocol. Accordingly, patients were added to the study to restore the original power and to allow comparison before/after corrective actions were taken. The final sample size is 83 evaluable subjects (166 evaluable eyes).Based on an updated dropout rate of 7%, the anticipated number of enrolled subjects is 89. Based on an updated screening rate of 23%, the anticipated number of screened subjects is 116.	
Number of sites	Three (3)-Four (4)	

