3.5.4. Exploratory efficiency endpoints

- The difference in the proportions of eyes with TBUT > 10 sec (i.e., not consistent with DED) at the follow-up, between eyes in the study arm and eyes in the control arm
- The difference in the proportions of subjects with OSDI < 23 (i.e., not consistent with DED) at the follow-up, between subjects in the study arm and subjects in the control arm
- The difference in eyelids appearance, as qualitatively evaluated by the study investigator, between eyes in the study arm and eyes in the control arm
- The difference in the *change* of MGS, between eyes in the study arm and eyes in the control arm
- The difference in the *change* of Meiboscore (Meibography), between eyes in the study arm and eyes in the control arm

3.5.5.Safety endpoints

- The difference in the incidence of non-ocular adverse events, between subjects in the study arm and subjects in the control arm
- The difference in the incidence of ocular adverse events, between subjects in the study arm and subjects in the control arm

QF-1044440 Rev. D Global Clinical Study Report Template GEN-0010523 Effective Date: July-2017

- The difference in the incidence of unanticipated serious adverse events, between subjects in the study arm and subjects in the control arm
- The difference in the level of pain/discomfort during IPL treatment, between subjects in the study arm and subjects in the control arm
- The difference in the level of pain/discomfort during MGX, between subjects in the study arm and subjects in the control arm
- The difference in the change of biomicroscopy immediately before and immediately after IPL treatment, between subjects in the study arm and subjects in the control arm

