5.1.5. Self-Assessment of Symptoms

To reduce the risk of bias, symptoms will be self-evaluated by the subject *before* any of the other specific tests (TBUT, MGS, and close-up photos of the eyelids) are performed by the study investigator(s).

Self-assessment of symptoms will be performed using 2 different methods:

- (1) Ocular Surface Disease Index (OSDI), using a questionnaire (developed by Allergan, Inc.) questionnaire. This questionnaire, which reports a single score for both eyes, is well-established for diagnosing symptoms of DED [30].
 - The questionnaire will be filled-out by the subject
 - The subject will grade 12 questions related to: ocular symptoms (3 questions), vision-related function items (6 questions) and environmental triggers items (3 questions)
 - Each of the 12 items will be scored from 0 to 4, where 0 indicates "never" and 4 indicates "always"
 - The questionnaire should take 5 minutes to complete.
 - OSDI will be calculated as the sum of the answered scores times 25, divided by the number of questions answered (range: 0 to 100).
 - Based on the OSDI, a subject can be categorized as having a normal ocular surface (0-12 points), mild symptoms (13-22 points), moderate symptoms (23-32 points), or severe symptoms (33-100 points), as described in [30].
 - OSDI at baseline is used for an inclusion criterion: to be included in the study, the subject must have OSDI ≥ 23 at baseline (moderate or severe symptoms).

QF-1044440 Rev. D	Global Clinical Study Report Template	GEN-0010523	Effective Date: July-2017

- (2) Eye Dryness Score (EDS), using a VAS. This questionnaire, which reports a single score for both eyes, has been used in other dry eye studies and was recently used as the primary symptom endpoint for FDA approval of lifitegrast for the treatment of signs and symptoms of dry eye (Xiidra, manufactured by Shire US, Inc.). EDS was accepted as a clinical outcome assessment by the division of transplant and ophthalmology at fda.gov (NDA 208073, June 2015)
 - The subject will be shown a 10 cm line, and will be asked to mark an X sign along the line
 - The subject will be instructed to mark the X sign on the leftmost side of the line if he/she does not have any symptoms of DED, on the rightmost side of the line if he/she has intolerable symptoms of DED, or somewhere along the line at a location that best represents his/her perception of symptoms in all other cases.

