	arm, where improvement is defined as a negative change of OSDI from BL to FU The improvement of EDS in the study arm is larger than the improvement of EDS in the control arm , where improvement is defined as a negative change of EDS from BL to the FU			
	 arm, where improvement is defined as a negative change of OSDI from BL to FU The improvement of EDS in the study arm is larger than the improvement of EDS in the control arm , where improvement is defined as a negative change of EDS from BL to the FU The difference in the proportion of eyes with normal TBUT (TBUT >10 sec) at FU, between eyes in the study arm and eyes in the control arm 			
Exploratory effectiveness	 arm, where improvement is defined as a negative change of OSDI from BL to FU The improvement of EDS in the study arm is larger than the improvement of EDS in the control arm , where improvement is defined as a negative change of EDS from BL to the FU The difference in the proportion of eyes with normal TBUT (TBUT >10 sec) at FU, between eyes in the study arm and eyes in the control arm The difference in the proportion of subjects with normal OSDI (OSDI < 23) at FU, between subjects in the study arm and subjects in the control arm 			
Exploratory effectiveness endpoints	 arm, where improvement is defined as a negative change of OSDI from BL to FU The improvement of EDS in the study arm is larger than the improvement of EDS in the control arm , where improvement is defined as a negative change of EDS from BL to the FU The difference in the proportion of eyes with normal TBUT (TBUT >10 sec) at FU, between eyes in the study arm and eyes in the control arm The difference in the proportion of subjects with normal OSDI (OSDI < 23) at FU, between subjects in the study arm and subjects in the control arm The difference in eyelids appearance, as qualitatively evaluated by the study investigator, between eyes in the study arm and eyes in the control arm 			

	• The difference in the change of MGS from BL to FU, between eyes in the study arm and eyes in the control arm				
	Throughout the study:				
	• the difference in the incidence of ocular adverse events, between subjects in the study arm and subjects in the control arm				
	 the difference in the incidence of non-ocular adverse events, between subjects in the study arm and subjects in the control arm 				
	• the difference in the incidence of unanticipated serious adverse events, between subjects in the study arm and subjects in the control arm				

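### The exploratory OSDI responder endpoint labels scores below 23 as normal, but the protocol's own scale ends the normal range at 12 and classes 13-22 as mild symptoms

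*Protocol*

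**What the plan says.** The exploratory endpoints in the Protocol synopsis include "The difference in the proportion of subjects with normal OSDI (OSDI < 23) at FU". The SAP synopsis uses the same label, "normal OSDI (OSDI < 23". Protocol 3.5.4 drops the word *normal* and makes a diagnostic gloss instead: "OSDI < 23 (i.e., not consistent with DED"; SAP 2.4 repeats it. Protocol 6.1.3 and SAP 4.1.3 give the < 23 cut-off with no label.

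Protocol 5.1.5 sets out how an OSDI score is to be read: "normal ocular surface (0-12 points), mild symptoms (13-22 points), moderate symptoms (23-32 points", with 33-100 as severe. The same section makes baseline OSDI of at least 23 an entry criterion, and Protocol 4.2.1 describes that range as moderate to severe symptoms.

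Neither document gives another definition of a normal OSDI or explains the difference.

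**The concern.** A follow-up score of 13-22 is mild symptoms under Protocol 5.1.5 and normal under the endpoint. Both cannot be right. The responder cut-off appears to be the entry cut-off reversed, so what it measures is whether a subject no longer meets the symptom entry criterion. That is a reasonable thing to report, but it is not normalisation.

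The companion TBUT endpoint in the same list is built on a different standard. Entry requires TBUT of 7 seconds or less, but the responder cut-off is above 10 seconds, in line with the limit of abnormality stated in Protocol 3.4.1 and SAP 1.1. A reader who sees *normal TBUT* and *normal OSDI* side by side will assume they were defined in the same way.

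What is at stake is the meaning of a reported proportion. If the SAP is followed as written, subjects with mild symptoms will be tabulated as normal.

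**Working it through.** The plan states no figure that depends on this cut-off, so there is nothing to reproduce. The check compares the cut-off with the protocol's bands, using the protocol's scoring rule.

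**Inputs (all from Protocol 5.1.5).** There are 12 items, each graded 0-4. "OSDI will be calculated as the sum of the answered scores times 25, divided by the number of questions answered". The bands are as quoted above, and entry requires OSDI of at least 23.

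**Attainable scores, 12 items answered, no rounding.** OSDI = 25 × sum / 12, so one item grade is worth 25/12 = 2.08 points.

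| Item sum | OSDI | Endpoint label | Band in Protocol 5.1.5 |
|---|---|---|---|
| 0-5 | 0 to 10.42 | normal | normal |
| 6 | 12.50 | normal | falls between 12 and 13 |
| 7-10 | 14.58 to 20.83 | normal | mild |
| 11 | 22.92 | normal | mild if the band runs up to 23; in a gap if it stops at 22 |
| 12 | 25.00 | not normal | moderate (lowest eligible score) |

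Twelve attainable scores (sums 0-11) lie below 23. Six of them (sums 0-5) are in the printed normal band. Sums 7-11 are above it on any reading, yet count as normal.

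**Distance to each cut from the lowest eligible score.**
- To OSDI < 23: from sum 12 (25.00) to sum 11 (22.92), which is one item grade.
- To the printed 0-12 band: from sum 12 to sum 5 (10.42), which is seven grades, or 7 × 2.08 = 14.58 points. If 12.5 were classed as normal, it would be six grades.

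**Unanswered items.** With m items answered, a sum of m gives exactly 25. A sum of m − 1 gives 25 − 25/m, which is below 23 whenever m < 12.5. With 6 to 12 items answered, that score runs from 20.83 to 22.92. The one-grade crossing therefore does not depend on complete questionnaires.

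**Rounding to whole numbers.** A sum of 11 becomes 23, which is eligible and not normal. The one-grade crossing then runs from sum 11 to sum 10 (20.83, rounded to 21). Sums 7-10 (15, 17, 19, 21) are still mild but labelled normal. The exact scores move; the contradiction stays.

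**Effect on the reported proportion.** In each arm, the proportion below 23 equals the proportion at 0-12 plus the proportion above 12 but below 23. The second term is the excess. With up to 83 completers randomised 1:1 (41 or 42 per arm), each such subject adds 1/42 to 1/41, about 2.4 percentage points. How many there will be cannot be calculated, because the documents give no OSDI distribution.

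**The case against.** The strongest reply is that this is a matter of wording. The cut-off is printed beside the label wherever the label appears, and Protocol 6.1.3 and SAP 4.1.3 give it with no label at all. The proportion below 23 is well defined and can be computed correctly. This stands as far as the arithmetic goes. It does not rescue the label, which is what a reader of the results will take away and which the protocol's own scale contradicts.

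Several stronger readings are tempting but not supported:

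- *The treatment comparison is biased.* The endpoint is a difference between randomised arms with the same entry criterion and the same cut-off. It is a fair comparison of proportions below 23; it is simply not a comparison of proportions normal.
- *Regression to the mean manufactures an effect.* Subjects selected at 23 or above will tend to drift down, and a cut-off placed at the entry limit makes crossing easy. That can raise the proportion in each arm, but it operates in both and does not by itself create a difference. It would also operate, with fewer crossings, under a 0-12 cut-off.
- *Subjects will be declared free of dry eye disease.* The gloss in Protocol 3.5.4 describes an OSDI score. Protocol 4.2 bases eligibility on symptoms and signs together, and TBUT is a separate endpoint. No section diagnoses a subject on OSDI alone.
- *One item grade is the typical size of the problem.* It is a boundary case for a subject at the minimum eligible score.

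The endpoint is also exploratory. Confirmatory inference on OSDI rests on the continuous change score (Protocol 3.5.3 and 7.2; SAP 2.3 and 5.2).

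**Conclusion.** The concern holds as an internal contradiction in a responder definition. By the scale in Protocol 5.1.5, the per-arm proportion reported as normal will be too high if any subject scores 13-22 at follow-up, by about 2.4 percentage points per such subject at the planned number of completers. The score-by-score figures assume unrounded scores and all 12 items answered; the contradiction itself depends on neither.

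The reach is limited. No bias in the between-arm difference is shown. The primary and secondary tests, the success criterion (Protocol 3.5.2, SAP 2.2) and the sample size (Protocol 7.3, SAP 5.3) are untouched. It is still worth correcting, because the definition is wrong as written and the data needed for the right one are already being collected.

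**What to change.** In both the Protocol and the SAP:

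1. Define *normal OSDI* at follow-up by the 0-12 band of Protocol 5.1.5, and report that proportion by arm.
2. State how non-integer scores are classed. The attainable score 12.5 falls between the printed normal and mild bands, and 22.9 falls between the printed mild and moderate bands, so give a rounding rule or continuous band limits.
3. Keep OSDI < 23 as a separate exploratory proportion, labelled as below the moderate-to-severe (entry) range.
4. Remove the word *normal* from the < 23 endpoint in both synopses, and the statement that it is not consistent with DED from Protocol 3.5.4 and SAP 2.4. Carry the same labels into Protocol 6.1.3 and SAP 4.1.3.

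The cost is a wording change, one more exploratory table row, and a *normal* proportion that will be lower if any subject scores 13-22. No new data are required. Relabelling the < 23 endpoint alone would remove the contradiction, but it would leave the study with no OSDI counterpart to the normal-TBUT endpoint.
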